Privacy will be protected by securing consent forms and storing in a secure location separate from the participants data in the lab. All other material will be labeled with subject number as oppose to subject's name. All biological samples will also be labeled with subject's number. The [name] Pain Lab is located in the basement of Logan Hall. Logan Hall has any number of ongoing experiments taking place from day to day. The basement of Logan Hall and the actual location of the Pain lab or relatively secluded. Therefore, participants can enter the pain lab with little worry that they will be identified as participating in this specific study. All research assistants have completed the CITI certification course and are sensitive to privacy issues and will therefore take necessary steps to ensure that the privacy of the participant is protected.

IV. Unanticipated Problems/Adverse Events

We will terminate the study in the event that a participant claims they have experienced significant psychological or physical distress lasting more than 1 hour in duration after study participation. The PI will also notify the IRB of any unanticipated problems within 24 hours.

V. Participant Complaints

Upon completion of the study, participants will be given a debriefing form, which will include study contact information. If the participants wish to gain more knowledge on the research they participated in, they may contact the PI of the study. When concerning complaints, the PI will consider each complaint very carefully and address them in a timely manner. However, if the complaint appears to be of a serious nature, the IRB will be contacted within 24 hours and the PI will consider halting the study.

STUDY DATA

I. Data Management Procedures and Confidentiality

Paper surveys will be used to collect basic demographic information. The paper surveys will be entered into an excel spreadsheet once data collection is completed. Data from the biological samples will be provided by the lab performing the analysis. The data from all of these sources will be combined into a single spreadsheet from which the data will be analyzed. All the paper-pencil data will be stored in a private area (i. e. locked storage cabinets within a locked lab) and the electronic data will be secured under password protection on secure lab computers/hard drives. All paper surveys, electronic files, and biological samples will be labeled using the participants subject number to ensure privacy and confidentiality.

Pregnancy tests will be used to assess pregnancy status of each of the female participants in order to exclude females that may be pregnant. In order to protect the confidentiality of each of the female participants, no identifying information will be written on any of the pregnancy tests. Upon completing the pregnancy test, if the test is negative, the pregnancy test will be disposed of and the subjects will be allowed to continue. If the participants test positive, they will be excluded from the study. No written record or reason for exclusion will be recorded and the positive pregnancy test with no identifying information on it will be disposed of and the research assistant will provide information on SHAC as described above.

After 5 years, all paper documents will be destroyed. All electronic data will be archived at the UNM Zimmerman Library. All data will be submitted to the library to be archived by archival specialist and made available to the public upon request. All data will be formatted according to the guidelines established by the Rocky Mountain Online Archive (RMOA).

II. Data Analysis/Statistical Considerations

Data analysis will be conducted using Multilevel Modeling to examine any potential differences across the experimental conditions. The pilot study used 12 participants. A power analysis was not carried out on the pilot study data due to the complication of conducting a power analysis using multilevel modeling. However, a prior power analysis conducted using the effect size reported in Chen, Decety, Huang, Chen, and Cheng (2016) used similar methods. Using these reported effects a sample size of 15 was adequate to find a significant effect with a power of 0.80 and an alpha of 0.05. The findings in the power analysis and the results from the pilot study, highly suggest that 15 participants will be sufficient in capturing significant results.

Participant Withdrawal

Subjects who decide to not participate in the study or who are otherwise ineligible for participation in the experimental protocol will be given the option to write a 5 page essay for the equivalent of 6 hours of research credit (for instructors who accept such credit).

Due to the expense and the complication of this study, if participants choose to withdraw, the researchers will process the biological samples and psychological data that were collected from the participants. This data will be used in subsequent analyses for this study. However, upon withdrawal if the participant would not like their biological or psychological data to be used for this study: they will be instructed to inform either the research assistants or the Principle Investigator for this study and their data will be excluded and their biological samples and psychological data will be destroyed.

PRIOR APPROVALS/REVIEWED AT OTHER IRBS

n/a

REFERENCES

Albert, D. J., Walsh, M. L., Gorzalka, B. B., Siemens, Y., & Louie, H. (1986). Testosterone removal in rats results in a decrease in social aggression and a loss of social dominance. *Physiology & behavior*, *36*(3), 401-407.

Beeman, E. A. (1947). The effect of male hormone on aggressive behavior in mice. *Physiological Zoology*, 373-405.

Berkley, K. J. (1997). Sex differences in pain. *Behavioral and Brain Sciences*, 20(03), 371-380.

Birnie, K. A., Noel, M., Chambers, C. T., von Baeyer, C. L., & Fernandez, C. V. (2010). The cold pressor task: Is it an ethically acceptable pain research method in children?. *Journal of pediatric psychology*, jsq092.

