The first part of the experiment will: a) examine basal levels of testosterone in females b) measure baseline pain tolerance) experimentally manipulate ephemeral (short-lasting) testosterone levels in females. The second part of the experiment takes place 4 hours later and consists of a pain task and behavioral measures/tasks. A double-blind protocol will be used so neither the researchers nor participants will know whether the participants were in the testosterone group or the placebo group until after the experimental procedures have been completed.

II. Study Procedures

Main Procedure

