The proposed study will consist of 2 experimental sessions where each participant will spend at most 5 hours per session. Prospective participants who meet our initial inclusionary criteria will come to the lab for a prelab session (See Appendix: Flow Chart of Experimental Procedures that Will Occur Over 4 Days for Each Participant). This session will be used to explain to the participants about the risks and benefits of participating in this study and to make sure they understand the time commitment. Once the prospective participants have read and stated they understand what is required of them, they will be allowed to sign the consent form and schedule their first lab visit. All lab visits will be determined based on the participant's menstrual cycle (See Appendix: Menstrual Cycle Scale). All female participants will visit the lab during their luteal phase of their menstrual cycle. The second lab visit will be 3 days after the first to ensure that the female participants are still in their luteal phase during the second lab visit. This will ensure that the changes in behavior and in pain are not the result of variations of within the menstrual cycle. At their first lab visit, participants will be pre-screened for pregnancy, tree nut allergies, and any use of drugs (e.g., Insulin, Blood-Thinners, Corticosteroids, Oxyphenbutazone, Triamcinolone) that may negatively interact with testosterone. After the first session, female participants will continue to be screened for pregnancy via a pregnancy test. Females who do test positive for pregnancy will be excused from the experiment and will be referred to the UNM Student Health and Counseling Center (SHAC) where they can seek further care. All participants will be inquired about any new medication use before the start of each session. Because exercise, sexual behaviors, and competitive activities may increase testosterone, all participants will be instructed to avoid these activities on the days that they participate in the experiment. Participants will also be asked to report the time they woke up in the morning to control for fluctuations in testosterone over the course of the day.

Participants will be randomly assigned to either a placebo group or a testosterone group before arrival. The experimenters will be blinded to this assignment. Randomization of the placebo and experimental drugs will be controlled by the research pharmacist.

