Participants will provide an initial salivary sample to establish baseline testosterone levels. Once they have given this sample, the participants will be given either the placebo or testosterone. They will then provide saliva samples 15 mins following the intervention. This will establish an intervention check. Baseline saliva sample before and after each intervention will be provided. Participants will remain in the lab for the duration of

this 5-hour session. They will be allowed to watch Netflix and listen to music as they wait. However, the content they can view or listen to will be limited to G or PG ratings in order to avoid fluctuation in their testosterone level. Participants will also be instructed to turn their cell phones off to ensure that their mood is not significantly altered. At 4 hours, participants will complete the post administration pain task. This pain task, like the behavioral measures, will only be administered once after 4 hours has passed. This is to prevent contamination and practice effect, which can occur when a behavioral task or measurement is administered multiple times during a session. The experimental sessions will take place 3 days apart. Participants will be reminded about their informed consent before their second session to ensure that they understand their continued rights as a research participant across the 2 experimental sessions. Participants will be awarded 3 research credits for each session for a total of 6 research credits. Participants will also be paid \$5 after completing each session for a total of \$10 for their participation.

Saliva Samples

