It is important to note, that the testosterone administration being proposed here is exactly the same to a previous study approved by this IRB (UNM Approval Code #902016-3). During the course of that previous study, none of the participants reported any ill effects from taking testosterone. With our previous experience, we feel that we can execute this protocol with minimum risk to the participants. The exact same researchers that worked on the previous study will also work on current study. These individuals will bring their experience and knowledge from the pilot study to this current study.

Compared to that previous study, this study is scaled down. Our Pilot study had 4 sessions consisting of 5 saliva samples per session. The current study, will only have 2 sessions with 2 saliva samples per session. The participants in the pilot study could receive the drug intervention (i.e. testosterone) twice during the course of the experiment. In the current study, they will only receive the drug intervention once. Therefore, the amount of risk to the participants is significantly reduced.

The pain component of this study is new, but our team has used this pain procedure in the past. In fact, we have published several papers using the ischemic pain task ([name] & Coulombe, 2011; [name] & Alcock, 2014; [name] [name], Trujillo, & Gangestad, 2014; [name], Rowell, & Lutz, 2014). Again, we feel confident that we can complete this protocol successfully with little risk to the participants.

I. *Target Population and Inclusion/Exclusion Criteria* College-aged females that are over the age of 18 and younger than 25 will be used for this study.

Exclusion Criteria:

All participants will be shown a list of exclusion criteria for this study on the Sona website. Before given the consent form the experimenter will go through this list to make sure the subjects do not meet any of the exclusion criteria. All women will be given a pregnancy test at each experimental session to ensure that the drug will not negatively impact an unborn child. If women are pregnant, they will be brought aside in the research lab and told they are pregnant and be given information on the Student Health and Counseling Center (SHAC) here on campus and excluded from the experiment. The following criteria will exclude a participant from the study:

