> Anyone that has a tree nut allergy. Females that are pregnant or may feel that they may be pregnant or breast-feeding. Anyone taking supplements that may influence their testosterone level. Anyone taking any kind of steroid that may increase his or her testosterone level. Anyone that smokes tobacco or uses smokeless tobacco. Anyone that reports any condition associated with nerve damage. Anyone that is using hormonal contraceptive.

Each participant will complete a Testosterone Pre-Screen form (see Appendix). This form will ask each participant individually whether they are taking any drugs or have any conditions that might be exacerbated by testosterone. This form will be completed before they participate sign the consent form and each time they arrive in the lab for an experimental session.

- II. Participant Enrollment Twenty Female Participants will be enrolled in this study.
- III. *Recruitment and Screening Procedures* Participants will be recruited via the UNM Psychology SONA system.
- IV. Informed Consent Process

The participants have several opportunities to decide whether to continue or to terminate their involvement. Solicitations will operate through the SONA system, in which prospective participants are fully informed of the study protocol. All participants will attend a pre-lab session where only the consent form will be discussed. The experimenter will go through the consent form and make sure that the participant understands all that is required of them before they sign the consent form. Students will thus be allowed up to two weeks prior to a scheduled start date to decide whether they would like to participate in this study. I am also freely available to answer questions and concerns. Prior to their involvement in the study (upon arrival to the study location), participants are expected to provide written consent for the overall study (See Consent Form).

V. Data Collection Procedures

Described above in the Main Experiment Procedure. Two saliva samples will be collected during each of the 2 sessions that each subject attends:

- 1. Pre-Experiment saliva
- 2. Post Testosterone administration at 15 mins

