Participants will also complete the pain task 4 hours following administration of T. Following the pain task, the behavioral measures will be administered at each experimental session to assess their state of aggression, risk-taking behavior, disgust, self-perceived health, self-perceived attraction, and sexual attitudes and beliefs. These surveys will be stored on an electronic survey site (Opinio) at UNM. We estimate that in all the experiment should take 5 hours to complete.

This same procedure will be repeated 3 days after the first experimental session.

VI. Study Timelines

The study will take approximately 12 months to complete starting from data collection and ending with the manuscript write up. It will take approximately 3 to 4 months to recruit and collect the data, and an additional month to 2 to 3 months to analyze the data and to process the biological samples, an additional month is needed to interpret the results, and finally and additional 3 to 4 months to prepare the manuscript write up. .

VII. Study Location(s)

The study will be conducted in the Pain Lab (Room B56) at Logan Hall on UNM Campus

VIII. Participant Compensation

Participants will be given 6 class credits (2 credits for 1st experimental session and 4 credits for the 2nd experimental session) for participation in this study and participants will be given \$5 for participating in each session of this study. Additionally, when participants preform the BART task they can earn between \$5 to \$20 per session. In total, participants can receive between \$10 and \$25 for each session they complete. In each session, participants will receive both the class credit and monetary compensation. The participants will be paid in cash. The class credit and the monetary compensation will be pro-rated based on the completion of each experimental session. If a participant fails to appear for an experimental session they will not be awarded credit or money for not showing up. If a participant decides to terminate the experiment during an experimental session they will be awarded credit and money for that session, but no further compensation will be provided if they do not complete the following experimental sessions. If participants terminate the session before they complete the BART, they will only be awarded the class credit for the session and the \$5.

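### The no-record rule for a positive pregnancy test makes no exception for a woman already dosed, so a first positive at session 2 would leave no written record of the result or of why she was excluded

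*Combined protocol and SAP*

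**What the plan says.** The rule is in STUDY DATA, I. Data Management Procedures and Confidentiality. A woman who tests positive is excluded, the unlabelled test is discarded, and "No written record or reason for exclusion will be recorded". The stated reason is confidentiality. The paragraph covers all female participants and does not distinguish a positive before dosing from one after it.

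Testing is repeated. The Exclusion Criteria section states: "All women will be given a pregnancy test at each experimental session to ensure that the drug will not negatively impact an unborn child". The Main Procedure section adds: "After the first session, female participants will continue to be screened for pregnancy via a pregnancy test".

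Dosing starts at session 1. After the baseline saliva sample, "the participants will be given either the placebo or testosterone" (Main Procedure). Data Collection Procedures then adds: "This same procedure will be repeated 3 days after the first experimental session".

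A woman with a positive test is told in private, referred to the student health centre and leaves the study. The principal investigator must notify the IRB of unanticipated problems within 24 hours (Unanticipated Problems/Adverse Events). Under Study Design, allocation is unknown to researchers and participants "until after the experimental procedures have been completed".

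**The concern.** Before any dose, keeping no record is sensible privacy protection: the woman has received nothing, and the study has no need of the information. After a dose the position differs. The test is there to protect an unborn child from the drug, and the session-2 test is the only one described that follows an administration. If that test turns positive, the plan as written directs staff to write nothing about it.

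At stake are traceability and what the woman can take to her own clinician. Without a record of the positive, nobody can later connect a pregnancy with the session-1 administration, and oversight depends on someone passing the news on by word of mouth. The visible text also has no step that offers her the one fact only the study holds, namely whether she received testosterone or placebo.

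**Working it through.** No arithmetic applies and the plan gives no figure to reproduce. The check is whether the rule reaches women already dosed, and whether other text makes an exception.

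1. **Order of events.** Test at session 1 (Exclusion Criteria); testosterone or placebo at session 1 (Main Procedure); test again at session 2, 3 days later (Main Procedure, Data Collection Procedures). A woman reaches the session-2 test only after a session-1 administration, so a first positive there always follows one.

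2. **Can a negative be followed by a positive?** The plan retests, so it allows for this. "All female participants will visit the lab during their luteal phase of their menstrual cycle", which is after ovulation, and the exclusion list includes "Anyone that is using hormonal contraceptive". These facts make the sequence possible. They do not give its frequency.

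3. **What was given.** Feasibility says the drug is received once, Potential Risks speaks of two doses, and Main Procedure describes assignment to a testosterone or a placebo group. On any of these readings, a woman at the session-2 test has had at most one active administration, and possibly only placebo. The text does not fix the probability of each.

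4. **What the rule removes and what it leaves.** It removes any record of the positive and of the reason for exclusion. It does not remove her individual prescription or the drug log (Testosterone Administration), the pharmacist's randomization (Main Procedure), or her session-1 samples and surveys, which carry her subject number.

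5. **Search for an exception.**
   - *IRB notice:* the wording is general and could cover this event. Pregnancy is not named. The duty falls on the principal investigator, whereas the data management section has a research assistant deal with the positive. No visible step passes the information from one to the other.
   - *Debriefing and contact with the investigator* (Participant Complaints): the form is given when the study is complete, and it is not described as disclosing allocation.
   - *Blinding statement:* it says when allocation may become known. It does not offer it to anyone.
   - *Drug log:* it tracks stock and use, not pregnancy or exclusion.

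None of these limits the no-record rule, so it applies to a woman already dosed.

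**The case against.** The strongest case against the point has four parts.

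**The exposure is documented elsewhere.** This is right. A reader might infer that a post-dose positive would vanish without trace, but the documents do not support that: prescription, log, randomization and session-1 data all survive. Only the positive result and the reason for exclusion go unrecorded.

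**The IRB clause already covers it.** The confidentiality rule can be read as keeping the result out of the study data, with the 24-hour duty running alongside. That reading is fair, and a general clause need not list every event. It works only if the principal investigator hears of the positive, and no visible step ensures that. The pilot's extra dose, reported to the IRB on discovery (Potential Risks), was a pharmacy error and a different kind of event; it shows that the team reports problems, not that this one would reach them.

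**The allocation point is an argument from silence.** This largely stands. A reader might infer that the woman would be refused her allocation. The text does not say so: her own procedures end when she is excluded, the blinding statement does not say that it runs until the last participant finishes, and she may contact the investigator. The consent pages, debriefing form, pharmacist letter and pre-screen form are not available and may settle the matter. All that can be said is that the visible text contains no express offer.

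**The rule is a deliberate privacy choice, and materiality is not shown.** Both are true. The participants are 20 students from one recruitment pool, and electronic data go to an archive open on request. Women who think they may be pregnant are already excluded. The documents give no event rate and no fetal-safety information, so neither harm nor likelihood can be claimed. These arguments set the size of the point. They do not explain why a rule that suits the period before dosing should also apply after it.

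**Conclusion.** The point holds in a limited form. As written, the rule leaves a first positive at session 2 without a written record of the result or of the reason for exclusion, although that woman received testosterone or placebo 3 days before. This follows from a rule the plan states, not from missing detail.

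It is a minor participant-safety and documentation matter and an optional improvement. The event is probably rare; no rate is given and none is assumed. A reader might infer a threat to the primary result, but the documents do not support one: at most an occasional session 2 would be missing without a stated reason, and the pain-tolerance analysis is otherwise untouched. Nor do they support a claim that the dose would harm a pregnancy.

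The conclusion assumes that each session's test precedes that session's dose, as its protective purpose implies, and that no unseen document limits the rule. The allocation part is conditional on the unseen consent and debriefing documents.

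**What to change.** Limit the no-record rule to positives found before any dose. For a positive after dosing:

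1. Make one coded paper entry (subject number, session, *positive test after dosing*) in the locked file. Keep it out of the analysis spreadsheet and the public archive, so that the existing destruction of paper documents after 5 years applies to it.
2. State that the research assistant tells the principal investigator, so that the existing 24-hour IRB clause applies.
3. Unless the consent or debriefing documents already provide it, let the woman obtain her allocation directly from the research pharmacist, so that the researchers stay blinded.

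Keep the practice of leaving the test itself unlabelled and discarding it.

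The cost is two or three sentences in the protocol and a matching line in the consent form. The downside is one coded sensitive record that the current plan avoids, in a sample of 20 where privacy matters; paper storage and the destruction date limit it. The change does not deal with a pregnancy first detectable after the session-2 administration, since no later test is described.
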